### **Listings**

- Patient demographics (FAS)
- Subject disposition (FAS)
- Dose administration record (FAS)
- Adverse events (FAS)
- Serious adverse events (Safety set)
- Adverse events leading to study drug discontinuation (Safety set)
- Adrenal hormone precursor accumulation-related AEs (Safety Set)
- Hypocortisolism-related AEs (Safety Set)
- Arrhythmogenic potential AEs (Safety Set)
- Pituitary tumour enlargement-related AEs (Safety Set)
- QT prolongation AEs (Safety Set)
- Laboratory values by patient (biochemistry/hematology) (Safety Set) \*
- Deaths (Safety Set)

---

Study Code: CLCI699C2X01B

Note that further outputs may be added as considered necessary.

### 2.3.1 Timing of interim analyses and design adaptations

Interim analyses have been performed by the CRO at the following time points:

- Q3 2021
- Q1 2022
- Q1 2023

Further time points might be added until the end of the study as needed.

## 2.4 STATISTICAL SOFTWARE

SAS version 9.4 or higher will be used in all analyses.

## 3 CHANGES IN THE PLANNED ANALYSIS OF THE STUDY

In this version the following changes have been added:

- To align the analysis plan with the amended Protocol version 02, the analysis of additional safety endpoints has been included.
- To comply with the PRAC request of adding to the PSUR of osilodrostat the available safety results of the study, corresponding interim analyses and relative times of analysis have been included.
- To identify data from parent studies to complete baseline visit (W1D1).

## 4 STATISTICAL METHODS

This section contains information that will be used to draft CSR Section 9.7 on statistical analysis.

### 4.1 DATA ANALYSIS GENERAL INFORMATION

The statistical analysis of these data will be performed in accordance with the data analysis section, Section 10, of the study protocol which is available in [Appendix 16.1.1 of the CSR]. Important information is given in the following sections and details are provided, as applicable, in [Appendix 16.1.9 of the CSR].

In summary and analysis tables of continuous variables, standard descriptive statistics (N, mean, standard deviation [SD], median, minimum and maximum) will be presented. The minimum and maximum statistics will be presented in summary tables to the same number of significant figures as the original data. The mean, median, will be presented to one more significant figure than the original data, while SD will be presented to an additional significant figure. For derived variables one figure will be presented for mean, median, minimum, maximum and 25th and 75th percentiles (where requested) and two figures for SD.

In summary tables of categorical variables, the number of non-missing observations by category will be presented with percentages. All percentages will be presented to one decimal place.

#### 4.1.1 General definitions

*Baseline*

---

Study Code: CLCI699C2X01B

For this study the baseline visit (W1D1) corresponds to the End of Treatment visit in the relative parent study.

The data for all assessments (except Obtain informed consent, Confirmation of Clinical Benefit from Study Treatment, and End of phase disposition) will be taken from the parent study.

#### *Study Treatment*

Study drug and investigational treatment refer to osilodrostat. Patients are to use the study treatment based on the parent protocol.

#### *Date of first/last administration of study drug*

The start date of study drug is defined as the first date when a non-zero dose of study drug was administered in the roll-over study and recorded on the Dosage Administration Record (DAR) eCRF.

The date of last administration of study drug is defined as the last date when a non-zero dose of study drug was administered and recorded on DAR eCRF.

#### *Date of first administration of study drug for total drug exposure*

For the calculation of the total drug exposure the start date of study drug is defined as the first date when a non-zero dose of study drug was administered in the parent study and recorded on the Dosage Administration Record (DAR) eCRF.

## **4.2 PATIENT DISPOSITION, DEMOGRAPHICS AND OTHER BASELINE CHARACTERISTICS**

### **4.2.1 Patient disposition**

Patient disposition will be summarized overall using the Safety Set. The number (%) of treated patients included in the Safety Set will be presented. The number (%) of patients in the Safety Set who are still on treatment, who discontinued the study treatment and the reason for discontinuation will be presented overall.

The following summaries will be provided (with % based on the total number of Safety Set patients):

- Number (%) of patients who are still on-treatment at the time of data cut-off or final data base lock;
- Number (%) of patients who discontinued the study treatment;
- Number (%) of patients with primary reason for end of study treatment (based on patient status entered in the 'Treatment Disposition' page);
- Number (%) of patients who have entered the post-treatment follow-up safety evaluation (based on the 'Study Disposition' page);
- Number (%) of patients who have discontinued from the post-treatment follow-up (based on the 'Study Disposition' page);
- Number (%) of patients with primary reason for end of study (based on patient status entered in the 'Study Disposition' page);

Listings will be provided overall and by indication and formulation for disposition, informed consent, inclusion/exclusion criteria using the Safety Set.

---

Study Code: CLCI699C2X01B

#### 4.2.2 Patient demographics and other baseline characteristics

Demographic information will be summarized and listed overall using the Safety Set. Demographic summary will include age and gender.

Categorical data (e.g., gender, age groups: <65 years, and ≥65 years) will be summarized by frequency counts and percentages. Continuous data (e.g., age) will be summarized by descriptive statistics (N, mean, median, standard deviation, minimum and maximum, 25th and 75th percentiles).

Demographic listing will include country, center, current patient ID, age and gender.

Medical history and ongoing medical conditions, including disease-related conditions and symptoms entered on (e) CRF will be summarized and listed overall. Separate summaries will be presented for ongoing and historical medical conditions. The summaries will be presented by primary system organ class (SOC) and preferred term (PT). Medical history and current medical conditions will be coded using the Medical Dictionary for Regulatory Activities (MedDRA) terminology. The MedDRA version used for reporting will be specified in the CSR and as a footnote in the applicable tables/listings.

A listing of parent study history (parent study number, parent patient ID) will also be provided using the Safety Set.

#### 4.3 *TREATMENTS (STUDY TREATMENT, RESCUE MEDICATION, CONCOMITANT THERAPIES, COMPLIANCE)*

##### 4.3.1 Study treatment / compliance

Dose administration data will be summarized overall using the Safety Set.

Dose adjustments and reason for adjustments will be summarized (by frequency and percentage) by dose reduction or dose interruption (or both). Doses at the time of reduction or interruption will be summarized by descriptive statistics (N, mean, median, standard deviation, minimum and maximum, 25th and 75th percentiles).

#### 4.4 *Measures for COVID-19 impact*

Given the nature of the study, currently it is not planned any specific adjustments impacting the analysis unless the amount of the COVID-19 related protocol deviations would become relevant.

The types of protocol deviations that were expected due to the impact of COVID-19 included changes in procedures, missing visits, planned visits not done at sites and patient discontinuations due to COVID-19 situation or patients' health status.

The list of the protocol deviations due to the COVID-19 is reported in the Protocol Deviation Management Plan and will be summarized overall and listed.

### 5 VARIABLES AND ENDPOINTS

Objectives and related endpoints are described in [Table 5-1](#) below altogether with the planned analysis of collected data.

Study Code: CLCI699C2X01B

Table 5-1 Objectives and related endpoints

Objective	Endpoint	Analysis
Primary		
To evaluate long term safety data, i.e., SAEs and AEs	Frequency and severity of AEs/SAEs	The assessment of safety will be based on the frequency and severity of adverse events (AEs) and serious adverse events (SAEs)
Secondary		
To evaluate clinical benefit as assessed by the investigator	Proportion of patients with clinical benefit as assessed by the investigator at scheduled visits	Proportion of patients with clinical benefit as assessed by the investigator will be summarized at scheduled visits
Other secondary		
To evaluate other safety data and tumor size	Lab parameters, vital signs, ECG, Tumor size and longest dimension	Shift tables vs Baseline and proportions of patients with notable abnormalities or grade 3 or 4

## 5.1 HANDLING OF MISSING DATA AND OUTLIERS

### 5.1.1 Study drug

Below mentioned imputation rules will be used in case of missing or partial end date of study drug.

#### Scenario 1

If the last date of study drug is after the cut-off date or is completely missing and there is no end of treatment eCRF page and no death date the patient should be considered to be on-going and use the cutoff date for the analysis as the last dosing date.

#### Scenario 2

If the last date of study drug is completely or partially missing and there is EITHER an end of treatment eCRF page OR a death date available, then imputed last dose date:

= 31DECYYYY, if only Year is available and Year < Year of min (EOT visit date, death date)

= Last day of the month, if both Year and Month are available and Year = Year of min (EOT visit date, death date) and Month < the month of min (EOT visit date, death date)

---

Study Code: CLCI699C2X01B

= min (EOT visit date, death date), for all other cases

The imputed date will be compared with start date of study drug.

If the imputed date < start date of study drug, then last date of study drug is set to start date of study drug; otherwise, use the imputed date.

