12.5.1 Safety endpoints

12.5.1.1 Analysis set and grouping for the analyses

For all safety analyses, the safety set will be used.

The overall observation period will be divided into two mutually exclusive segments:

1. on-treatment period: from day of first dose of study medication in this study to 30 days after last dose of study medication
2. post-treatment period: starting at day 31 after last dose of study medication.

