## 7.3 EXTENT OF EXPOSURE

Definitions of duration of exposure, cumulative dose, average daily dose, as well as intermediate calculations, include:

Osilodrostat:

- Duration of exposure (weeks): (min (last date of rollover study drug, date of death, date of data cut-off) – first date of rollover study drug + 1)/7
- Cumulative dose (µg): total dose of study drug taken by a patient in the rollover study
- Number of dosing days (days): duration of exposure \*7 – number of zero dose days
- Average daily dose (µg/day): cumulative dose (µg) / number of dosing days (days)

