### 7.4.1 Adverse events (AEs)

Treatment emergent AEs are defined as those that started on or after the study medication, or those that started before study medication but worsened afterwards. AEs starting after 30 days after last dose of Osilodrostat treatment are not considered treatment emergent AEs.

Summary tables for adverse events (AEs) have to include only AEs that started or worsened during the on-treatment period, the treatment-emergent AEs. However, all safety data (including those from the post-treatment periods) will be listed and those collected during the post-treatment period are to be flagged.

The incidence of treatment-emergent adverse events (new or worsening from baseline) will be summarized by system organ class and/or preferred term, severity based on CTCAE grades (version 4.03 or higher), type of adverse event, relation to study treatment. The summary will include AEs regardless of study-drug relationship. The same analysis will be repeated for SAEs.

All treatment emergent AEs and SAEs will be listed. In this listing, the information on the relationship to study treatment will be included.

---

Study Code: CLCI699C2X01B

Adverse events will be coded using the Medical dictionary for regulatory activities (MedDRA) terminology using the latest available MedDRA version at the time of the analyses and the information of MedDRA version will be specified in the footnote of relevant outputs.

The following selection of AEs will be listed and summarized separately using Safety Set. AEs will be summarized for all grades and for grade 3 or 4 side-by-side.

- AEs
- SAEs
- AEs leading to study drug discontinuation
- AEs requiring dose adjustment or interruption
- AEs requiring additional therapy
- Adverse events of special interest (AESI)

For the legal requirements of ClinicalTrials.gov and EudraCT, two required tables on treatment-emergent adverse events which are not serious adverse events with an incidence greater than 2% and on treatment-emergent serious adverse events and SAE suspected to be related to study treatment will be provided by system organ class and preferred term on the Safety Set population.

If for a same patient, several consecutive AEs (irrespective of study treatment causality, seriousness and severity) occurred with the same SOC and PT:

- A single occurrence will be counted if there is  $\leq 1$  day gap between the end date of the preceding AE and the start date of the consecutive AE

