#### 7.4.2 Laboratory parameters

Laboratory data summaries will include all assessments available for the lab parameters collected no later than 30 days of safety follow-up whichever is later after the last study treatment administration date using data from all sources. All laboratory assessments will be listed and those collected later than 30 days after the last study treatment date will be flagged in the listings.

Grading of laboratory values will be assigned programmatically as per NCI Common Terminology Criteria for Adverse Events (CTCAE) version 4.03 or higher. The calculation of CTCAE grades will be based on the observed laboratory values only, clinical assessments will not be taken into account. CTCAE version 5.0 will be applied and an extract of the tests that can be graded is reported in attachment 8.3.

CTCAE Grade 0 will be assigned for all non-missing values not graded as 1 or higher. Grade 5 will not be used. For laboratory tests that are graded for both low and high values, summaries will be done separately and labeled by direction, e.g., sodium will be summarized as hyponatremia and hypernatremia.

---

Study Code: CLCI699C2X01B

For laboratory tests where grades are not defined by CTCAE, results will be categorized as low/normal/high based on laboratory normal ranges.

For laboratory tests where grades are defined by CTCAE:

- Summary table for AEs of grades 3 or 4
- Shift tables using CTCAE grades to compare baseline to the worst on-treatment value
- Worst post-baseline CTCAE grade (regardless of the baseline status). Each patient will be counted only once for the worst grade observed post-baseline

For laboratory tests where grades are not defined by CTCAE,

- Shift tables using the low/normal/high/ (low and high) classification to compare baseline to the worst on-treatment value

The following listings will be produced for the laboratory data (hematology, and biochemistry):

- Listing of all laboratory data with values flagged to show the corresponding CTC grades the classifications relative to the laboratory reference ranges
- Listing of notable laboratory abnormalities (i.e., CTC grade 3 or 4 laboratory toxicities).

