#### 7.4.6 Deaths

Separate summaries for on-treatment death and all deaths (*including* on-treatment and post-treatment) will be produced by primary system organ class and preferred term overall using the Safety Set. On-treatment and all deaths will be listed overall, and post treatment deaths will be flagged.

Study Code: CLCI699C2X01B

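### The SAP's last-dose imputation discards a known month when the end-of-treatment visit or death falls in a later calendar year, and so places the last dose after the month on record

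*SAP*

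**What the plan says.** SAP 5.1.1, Scenario 2, applies when the last-dose date is wholly or partly missing and an EOT page or a death date exists. The reference date is the earlier of the EOT visit and death. There are three branches:

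1. Only the year is known and it precedes the reference year: 31 December of the recorded year.
2. "Last day of the month, if both Year and Month are available and Year = Year of min (EOT visit date, death date"), and the recorded month precedes the reference month.
3. "min (EOT visit date, death date), for all other cases".

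One check follows: "The imputed date will be compared with start date of study drug". It moves an imputed date forward if it precedes the start of treatment. There is no upper check against the recorded month.

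The last-dose date is then used in four places:

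- SAP 7.3: duration of exposure runs to "min (last date of rollover study drug, date of death, date of data cut-off"), and the number of dosing days is derived from it.
- SAP 7.4.1: "AEs starting after 30 days after last dose of Osilodrostat treatment are not considered treatment emergent AEs".
- SAP 7.4.2: laboratory summaries use the same 30-day limit, and "those collected later than 30 days after the last study treatment date will be flagged in the listings".
- SAP 7.4.6: "Separate summaries for on-treatment death and all deaths" are planned. Protocol 12.5.1.1 defines the on-treatment period as "from day of first dose of study medication in this study to 30 days after last dose of study medication".

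**The concern.** A record with month and year known, in a year before the reference year, satisfies neither specific branch. Branch 1 needs the month to be unknown, and branch 2 needs the years to be equal. The record drops to the catch-all, which returns a date the record itself rules out.

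The SAP's own conventions suggest this is an oversight. Within one calendar year the same gap gives month-end. With less information (year only) the answer is year-end, which can be earlier and closer to the truth than the answer given when the month is also known. The adverse-event start-date rules in SAP 5.1.2 (Table 5-3) do cover an earlier year with a known month.

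In a study whose purpose is long-term safety, the last-dose date fixes the end of exposure and decides which events, laboratory values and deaths count as on treatment. An imputed date that is too late stretches all of these.

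**Working it through.** The plan gives no figure to reproduce, so the check applies the three branches literally. It compares them with the same rule in which branch 2 asks only whether the recorded year-month precedes the reference year-month. All dates below are illustrative.

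**Worked cases**

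| Recorded last dose | Reference date (EOT) | SAP as written | Year-month comparison | Excess (days) |
|---|---|---|---|---|
| Nov 2019 | 15 Jan 2020 | 15 Jan 2020 | 30 Nov 2019 | 31 (Dec) + 15 = 46 |
| Dec 2020 | 8 Mar 2021 | 8 Mar 2021 | 31 Dec 2020 | 31 + 28 + 8 = 67 |
| Dec 2023 | 15 Jan 2024 | 15 Jan 2024 | 31 Dec 2023 | 15 |
| Oct 2021 | 20 Jan 2022 | 20 Jan 2022 | 31 Oct 2021 | 30 + 31 + 20 = 81 |
| Oct 2021 | 20 Dec 2021 | 31 Oct 2021 | 31 Oct 2021 | 0 |
| Nov 2020 | 15 Dec 2020 | 30 Nov 2020 | 30 Nov 2020 | 0 |
| 2021 only | 20 Jan 2022 | 31 Dec 2021 | 31 Dec 2021 | 0 |

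With EOT on 20 January 2022, the less complete record (2021) gives 31 December 2021 and the more complete one (October 2021) gives 20 January 2022.

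**Is it systematic?** Take an assumed first dose of 1 March 2019, every reference date in 2021 to 2023, and every recorded month from March 2019 up to the month before the reference. That makes 43,281 combinations. The rule as written lands after the recorded month in all 37,230 with an earlier recorded year (smallest excess 1 day), and in none of the remaining 43,281 − 37,230 = 6,051 with the same year.

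**Effect on exposure and the 30-day window.** For October 2021 with EOT on 20 January 2022 and first dose on 1 March 2019:

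- Exposure as written is 1,057 / 7 = 151.0 weeks. With month-end it is 976 / 7 = 139.4 weeks.
- The treatment-emergent window closes on 19 February 2022 as written, and on 30 November 2021 with month-end.

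**Effect on deaths.** If death is the reference date, the catch-all sets last dose equal to death, so the death is always on treatment. Last dose October 2021 with death on 20 January 2022 counts as on treatment as written; with month-end the window closed on 30 November 2021. Last dose August 2021 with death on 20 November 2021 is post-treatment under the SAP's own month rule, because that window closed on 30 September 2021. Two similar histories are classified differently because one crosses New Year.

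**How often a day-missing date would be hit.** The documents do not give the interval from last dose to EOT, so it is assumed fixed at four values. The largest is the 12-week visit interval plus the 2-week window (98 days). Every last-dose day from 1 January 2019 to 31 December 2022 (1,461 days) is used once. A date is affected if the interval crosses 31 December, which is 4 × gap out of 1,461.

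| Assumed gap (days) | Affected | Share | Mean excess (days) | Range |
|---|---|---|---|---|
| 7 | 28 / 1,461 | 1.9% | 4.0 | 1–7 |
| 28 | 112 / 1,461 | 7.7% | 14.5 | 1–28 |
| 84 | 336 / 1,461 | 23.0% | 70.3 | 54–84 |
| 98 | 392 / 1,461 | 26.8% | 83.9 | 68–98 |

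These are shares of day-missing last-dose dates, not of patients.

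**A separate minor point.** SAP 5.2.2 defines study day before treatment as first dose date minus event date, which is positive. With first dose on 10 June 2019, an event on 9 June has study day 1, and so does 10 June. No planned summary is stated to use study day, so this affects display only.

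**The case against.** The strongest reply is that the rule will rarely be used. The day must be missing while month and year are present, it must still be missing at lock, and the EOT or death date must fall in a later year. Protocol 6.5.1.1 requires dose changes to be recorded, and Protocol 11.2 tracks dispensing and dosage changes through the IRT and queries missing values before lock. This stands: the count is probably small, and the documents give no way to estimate it.

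The long assumed gaps are also open to challenge. Twelve weeks separates on-treatment visits, whereas Protocol section 8 asks for a prompt final visit after premature discontinuation. That favours the shorter gaps, although no limit is set. Likewise, the December 2023 case puts an EOT visit after the date to which Protocol 3.1 expects the study to stay open in the UK. It is only an illustration of a closing date at a year boundary.

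The consequences are bounded too. No hypothesis is tested and no exposure-adjusted event rate is planned. A longer window only moves events into the treatment-emergent tables, and all safety data are listed in any case. Protocol 10.1.3 limits reporting of SAEs more than 30 days after treatment to those suspected to be related. Any zero-dose days recorded after stopping would be subtracted from the number of dosing days in SAP 7.3, though not from duration of exposure.

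These arguments limit the size of the effect. None shows that the rule returns a possible date. The SAP wrote it for dates that stay partial, so it has to be right when it is used.

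**Conclusion.** The concern holds. As written, SAP 5.1.1 imputes an impossible last-dose date whenever month and year are known and the year precedes that of the EOT visit or death. Neither the start-date check nor the cap at death or data cut-off in SAP 7.3 restores the recorded month.

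Per affected patient, the excess was 15 to 81 days in the worked cases that cross a year boundary. It averaged 4.0 to 83.9 days across the assumed gaps of 7 to 98 days, and the lower end is more plausible if final visits are prompt. Duration of exposure and the 30-day windows lengthen by at least the number of days past month-end. The effect on the whole trial cannot be quantified, because the number of day-missing dates is not given, and it is probably small. The rule should still be corrected before the final analysis, because the error is certain where it applies and costs almost nothing to remove.

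**What to change.** Reword the second branch so that year and month are compared together: *impute the last day of the recorded month whenever year and month are both known and that year-month is earlier than the year-month of the reference date (the earlier of EOT visit and death)*. Keep the 31 December branch, the catch-all and the start-date check as they are. This extends the SAP's own month-end convention across the year boundary and leaves every same-year result unchanged.

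At the same time, define study day before treatment in SAP 5.2.2 as event date minus first dose date, so that the day before first dose is −1.

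The cost is one SAP sentence for each point and a one-line program change for the imputation. No new data are needed.
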